## I. LIST OF ABBREVIATIONS

APDP Advanced Pain Discovery Platform

BMI Body Mass Index

BPI Brief Pain Inventory
CI Chief Investigator

CIPN Chemotherapy-Induced Peripheral Neuropathy

CNORIS Clinical Negligence and Other Risks Insurance Scheme

CPG Chronic Pain Grade

GoDARTS Genetics of Diabetes Audit and Research Tayside Study

DN4 Douleur Neuropathique En 4 Questions

DPN Diabetic Peripheral Neuropathy

EORTC-CIPN20 European Organisation for Research and Treatment of Cancer -

Chemotherapy-Induced Peripheral Neuropathy 20-item Questionnaire

EQ5D-5L Euroquol 5 Dimensions-5 Levels

EU European Union FIB Fluid Biomarker

GCP Good Clinical Practice
GP General Practitioner

GS:SFHS Generation Scotland: Scottish Family Health Study

GWAS Genome-Wide Association Study

HDL High-Density Lipoprotein
HIC Health Informatics Centre
HRA Health Research Authority

IRAS Integrate Research Application System

ISRCTN International Standard Randomised Controlled Trials Number

LSC Life Sciences Compute

MNSI Michigan Neuropathy Screening Instrument

NHS National Health Service
NRS Numerical Rating Scale

PAINSTORM Partnership for Assessment and Investigation of Neuropathic Pain: Studies

Tracking Outcomes, Risks and Mechanisms

PCS Pain Catastrophizing Scale

PIS Patient Information Sheet

PROMIS Patient-Reported Outcomes Measurement Information System

REC Research Ethics Committee

RNA Ribonucleic Acid

SAP Statistical Analysis Plan

SEM Structural Equation Modelling

SF-4a Short Form-4 Answers

SGPALS Saltin-Grimby Physical Activity Level Scale

SIMD Scottish Index of Multiple Deprivation

SNP Single Nucleotide Polymorphism SOP Standard Operating Procedure

STM Senior Trial Manager

TASC Tayside Medical Science Centre

TCTU Tayside Clinical Trials Unit

TIPI Ten Item Personality Inventory

TMF Trial Master File

TMG Trial Management Group

TRE Trusted Research Environment

## II. STUDY SUMMARY

Study Title	PAINSTORM: Partnership for Assessment and Investigation of Neuropathic Pain: Studies Tracking Outcomes, Risks and Mechanisms. Dundee Epidemiology study.		
PAINSTORM is a collaborative programme, led by the University of Oxford. Partners in the PAINSTORM consortium are the University of Oxford, Imperial College (London), the University of Dundee, the University of Aberdeen, and Ghent University.  This protocol covers the epidemiology study being led by the University of Dundee: PAINSTORM Dundee Epidemiology study			
Study Design	Observational		
Study Participants	Cohort 1, UK: UK-Biobank Cohort 2, Scotland: SHARE (Scottish Health Research Registry) people with diabetes mellitus, people who have received potentially neurotoxic chemotherapy. Cohort 3, Scotland: GoDARTS (Genetics of Diabetes Audit and Research) people with diabetes mellitus		
Planned Sample Size	Cohort 1: 173,000 Cohort 2: 6,194 Cohort 3: 1,915		
Follow up duration	duration Cohort 1: 36 months Cohort 2: 18 months Cohort 3: 72 months		
Planned Study Period	Period 5 years		
	Objectives Outcome Measures		
Primary	In people with diabetes, and/or who have received potentially neurotoxic chemotherapy, what clinical, psychosocial, demographic and genetic factors are associated with the presence of neuropathic pain at baseline and onset, worsening or remission of neuropathic pain after follow-up	MNSI/EORTC-CIPN20 questionnaires Chronic pain identification questionnaire DN4 questionnaire List of body sites	

Secondary

of up to 5 years?

See section 3.4

See section 3.4

## III. FUNDING AND SUPPORT IN KIND

FUNDER(S)

The Advanced Pain Discovery Platform (APDP) – a 5-year initiative funded through the Government's Strategic Priorities Fund and delivered in partnership through UK Research and Innovation (Medical Research Council, Economic and Social Research Council, Biotechnology and Biological Sciences Research Council), Versus Arthritis and Eli Lilly.

## IV. ROLE OF STUDY SPONSOR AND FUNDER

The roles and responsibilities of the Sponsor and Funder will be detailed in the Clinical Research Agreement and Co-Sponsor Agreement.

# V. ROLES AND RESPONSIBILITIES OF STUDY MANAGEMENT COMMITEES/GROUPS & INDIVIDUALS

The Chief Investigator (CI) will be responsible for the conduct of the study. Site delegate(s) will oversee the study and will be accountable to the CI.

The study will be conducted in accordance with the principles of Good Clinical Practice (GCP).

In addition to Sponsorship approval, a favourable ethical opinion will be obtained from an appropriate NHS REC. Appropriate NHS R&D permission(s) will be obtained prior to commencement of the study.

The study will be co-ordinated by a Trial Management Group (TMG), consisting of the CI and Co-Investigators (Co-I), Study Coordinator, Senior Trial Manager (STM), Senior Research Statistician and Patient Partner(s). Other members will be added as appropriate. Minutes of the TMG will be maintained in the Trial master File (TMF).

## VII. KEY WORDS

[figure not shown]
Neuropathic pain, genomics, epidemiology, neuropathy, chemotherapy induced peripheral neuropathy, diabetes.

## VIII. STUDY FLOW CHART

[figure not shown]
## **Cohort 1: UK Biobank**

## **Cohort 2: SHARE**

## **Cohort 3: GoDARTS**

#### 1. BACKGROUND

Neuropathic pain (NeuP) arises due to injury to the somatosensory nervous system^1. NeuP is common affecting 7-10% of the population. Crucially, not everyone with such an injury develops significant NeuP, and those who do develop it include a wide range of severity, impact, and outcomes. This variation in pain prevalence/severity involves a complex interaction between genetic, environmental and clinical factors. The exact contribution and interaction of these risk/protective factors is currently unknown, but vital to understand, so that treatment and prevention can be informed. Prevalence of NeuP is projected to increase due to aging population, the diabetes/obesity epidemic and cancer survival. Unfortunately, the management of NeuP is inadequate due to poor efficacy and tolerability of current therapies. First-line therapy is usually analgesic medication, although psychological strategies and neuromodulation are applied in specialist settings. Major unmet needs for the field include: ability to predict NeuP to institute preventive strategies; understanding how best to individualise existing therapies; and improving translation from promising preclinical therapies to the clinic. Such translation requires better human cellular models, improved NeuP biomarkers and trial ready stratified cohorts. The molecular, physiological and psychosocial factors underlying NeuP are too often studied in isolation and targeted as silos.

The PAINSTORM consortium is a collaboration of leading researchers in the field of NeuP/genomics/epidemiology and neuropathy, from the UK (Universities of Oxford, Dundee and Aberdeen, Imperial College London) and Belgium (University of Ghent), and Patient Insight Partners, who are people living with NeuP. Its aim is to understand NeuP pathophysiology in terms of risk factors and protective mechanisms ranging from molecular pathways to social factors, and to apply this in order to improve outcomes.

This protocol is for one component which will be led by the University of Dundee (PAINSTORM Dundee Epidemiology Study).

### 2. RATIONALE

This study follows on from the successful DOLORisk study, which identified genetic and nongenetic factors associated with the presence, onset, progression and remission of NeuP, in a combination of cohort studies including population, diabetic population and specialist clinical populations. In particular, DOLORisk Dundee examined two Scottish populations (Generation Scotland: the Scottish Family Health Study [GS:SFHS], and the Genetics of Diabetes Audit and Research, Tayside Scotland study [GoDARTS]. Findings from DOLORisk Dundee have been presented at national and international conferences, and are the subject of scientific papers in advanced preparation or under review. They include identification of at least one new genetic variant found to be associated with the presence of NeuP, and clinical, psychological and sociodemographic factors found to be associated with onset, worsening or remission of NeuP over time. This was the first population-based longitudinal study of NeuP. In addition, comprehensive and systematic reviews, conducted as part of DOLORisk, identified all genetic and non-genetic factors known to be associated with the presence of NeuP.

These findings, though, need to be confirmed in other populations, and/or in cohorts with longer follow-up periods. PAINSTORM Dundee Epidemiology, therefore, aims to test their validity and seek other, previously unidentified associations, focusing on two conditions that confer a high risk of developing NeuP – diabetes and chemotherapy treatment. We will work with three cohorts: (1) UK Biobank, a general population cohort which has recently been re-phenotyped for pain, including NeuP; (2) members of SHARE Scotland with diabetes and/or who have received potentially neurotoxic chemotherapy; SHARE is a register of people who have volunteered to be contacted for potential research participation; and (3) members of the GoDARTS cohort who have diabetes, and who participated in the baseline and 18-month follow-up survey of DOLORisk Dundee.

## 2.1. Assessment and Management of Risk

In this observational study there is no risk from an intervention. The development of PAINSTORM was a partnership between clinicians, scientists and people living with NeuP. PAINSTORM Dundee Epidemiology will continue to be managed, and its outputs co-created by this grouping.

#### 3. OBJECTIVES AND OUTCOME MEASURES/ENDPOINTS

## 3.1. Hypothesis

In the presence of diabetes and/or potentially neurotoxic chemotherapy, an individual's risk of developing NeuP and its outcomes can be predicted by specific psychosocial, genetic and clinical risk factors.

#### 3.2. Aims

The ultimate aim of the PAINSTORM consortium is to reach a new understanding of NeuP, by combining molecular, physiological and psychological approaches to describe its development and progression. An inter-disciplinary approach will be used to determine the interaction of these different factors (with 'biological' and 'psychosocial' factors given equal weight) and develop innovative technologies and person-centred outcome measures to identify these pathophysiological processes in patients. The PAINSTORM Dundee Epidemiology study will contribute to this, at population level, focusing on people with diabetes and/or receiving potentially neurotoxic chemotherapy.

#### 3.3. Primary objective

In people with diabetes, and/or who have received potentially neurotoxic chemotherapy, what clinical, psychosocial, demographic and genetic factors are associated with the presence of NeuP at baseline and onset, worsening or remission of NeuP after follow-up of up to 5 years?

#### 3.4. Table of endpoints/outcomes

Objectives	Outcome Measures	Timepoint(s) of evaluation
Primary Objective Presence of NeuP/neuropathic descriptors		Cohort 1: 2019/20

	Chronic pain identification questionnaire	Cohort 2: 2022 and 2023/24 Cohort 3: 2017, 2018/19,
	DN4 questionnaire	2021/22
	List of body sites	
	Michigan Neuropathy Screening Instrument (Cohorts 1, 2- diabetes group and 3)	
	European Organisation for Research and Treatment of Cancer - Chemotherapy- Induced Peripheral Neuropathy 20-item questionnaire (EORTC- CIPN20; Cohort 2- chemotherapy group)	
Secondary Objectives Severity of pain		
Severity of pain	Chronic Pain Grade (CPG) questionnaire	Cohort 2: 2022 and 2023/24
	Brief Pain Inventory (average)	Cohort 3: 2017, 2018/19 (CPG only), 2021/22 (CPG only)
Quality of life	EQ5D-5L questionnaire	Cohort 1: 2019/20
		Cohort 2: 2022 and 2023/24
		Cohort 3: 2017, 2018/19, 2021/22
Psychological health	PROMIS Depression Score	Cohort 2: 2022 and 2023/24
	PROMIS Anxiety Score	Cohort 3: 2017, 2018/19
	PROMIS Sleep Score	(PROMIS only), 2021/22
	PROMIS Support	(PROMIS only)
	TIPI Personality questionnaire	
	Pain Catastrophising scale	
	Adverse Childhood Experiences	
Lifestyle	Smoking questionnaire	Cohort 2: 2022 and 2023/24
	Alcohol questionnaire	Cohort 3: 2017
	Saltin-Grimby Physical Activity Level Scale (SGPALS)	

	Gender	Cohort 2: 2022 and 2023/24
	Ethnicity	Cohort 3: 2021/22
	SIMD	
	Weight	
	Height	
	Years in full-time education	
	Working status	
	Household income	
Clinical	Diabetes/Chemotherapy	Cohort 2: 2022 and 2023/24
	Duration	Cohort 3: 2021/22
	Diabetes Type	

### 4. STUDY DESIGN

This is a population-based, prospective epidemiological study, focusing on identifying and replicating genetic and environmental risk factors for developing NeuP in people with diabetes and/or who have received potentially neurotoxic chemotherapy, and predicting its outcomes (remission or exacerbation). The identification of NeuP and pain-related traits and comorbidities will mainly be achieved through longitudinal survey-based questionnaires of three cohorts, UK Biobank (general population), GoDARTS (diabetes, mainly Type 2) and SHARE (general population).

#### 5. STUDY SETTING

Cohort 1: UK Biobank, UK wide.

UK Biobank is a large-scale biomedical database and research resource, containing in-depth genetic and health information from half a million UK participants aged 40-69 years, who were registered with a GP within the NHS and recruited between 2006 and 2010. The UK Biobank data relating to NeuP, including those arising from the pain re-phenotyping exercise conducted in 2019-20 and the projected follow-up in 2024 will be accessed (UK Biobank Application 49572). This will include genomic and non-genomic data, particularly relating to participants known to have diabetes.

PAINSTORM has approval to access the phenotypic and genetic data that are available for all participants (UK Biobank Application 49572; REC Reference 21/NW/0157).

Cohort 2: SHARE. Scotland wide.

SHARE is a register of people aged 11 and over, interested in participating in health research and who agree to allow SHARE to use data in their various NHS electronic records to check whether they might be suitable for health research studies. The Health Informatics Centre (HIC) Dundee, a Nationally Accredited, ISO27001 certified Safe Haven, hosts SHARE and provides an environment which protects data confidentiality and ensures secure management

and processing of data. Participants in SHARE who are identified as having diabetes or who have received potentially neurotoxic chemotherapy for cancer will be invited to complete a baseline questionnaire identifying the presence or absence of NeuP and a similar follow-up questionnaire approximately 18 months later (2022 and 2023/24).

Cohort 3: Genetics of Diabetes Audit and Research Scotland cohort (GoDARTS), Tayside region.

GoDARTS is funded by the Wellcome Trust, supported by Diabetes UK and has consented patients with type 2 diabetes (over 10,000 individuals) and matching controls (over 8,000 individuals) throughout Scotland. Members attend for baseline clinical, biochemical and lifestyle assessment, and have provided consent for linkage of their data to routine NHS records. They have also provided consent to be re-contacted for future research participation. A total of 1,046 GoDARTS participants (with diabetes) completed the DOLORisk study questionnaires identifying the presence or absence of NeuP at two time points, approximately 18 months apart (2017 and 2018/19), allowing assessment of the development, exacerbation or improvement of NeuP. These individuals (unless lost to follow-up) will be invited to participate in one further follow-up questionnaire study as part of PAINSTORM Dundee Epidemiology.

#### 6. PARTICIPANT ELIGIBILITY CRITERIA

#### 6.1. Inclusion criteria

Cohort 1: UK Biobank 18 years or older

Completion of re-phenotyping exercise 2019/20

Cohorts 2 & 3: SHARE & GoDARTS

18 years or older

Existing consent to be re-contacted.

Identified as being currently alive.

Currently has a phone number, email or postal address on file

AND either:

People on the SHARE register (Cohort 2) with Diabetes Mellitus and/or who have received potentially neurotoxic chemotherapy for the treatment of cancer Or

People on the GoDARTS register (Cohort 3) who responded to two questionnaires for the DOLORisk Dundee study (REC reference: 15/YH/0285)

#### 6.2. Exclusion criteria

Cohorts 1, 2 & 3: Nil

### 7. STUDY PROCEDURES

#### 7.1. Recruitment

## 7.1.1. Participant identification

#### Cohort 1

UK Biobank data relating to NeuP, including those arising from the pain re-phenotyping exercise conducted in 2019-20 and the projected follow-up in 2024 will be accessed via the online Access Management System. Approvals are already in place for PAINSTORM to access and analyse the UK Biobank phenotypic and genetic data that are available for all participants (REC Ref: 21/NW/0157, UK Biobank Project: 49572)

### Cohorts 2

Potentially eligible people registered on SHARE will be identified by HIC. Participants contact information is held confidentially and securely by the joint GoDARTS/SHARE administration team. Prior to invitations being sent, HIC will identify people who are participants in both GoDARTS and SHARE, to ensure that those people are not included in the study twice. If someone is included in both registers, they will be invited to take part as per Cohort 3. Where someone in SHARE is identified as having both diabetes and potentially neurotoxic chemotherapy, they will be invited to participate as part of the chemotherapy group.

Potential participants will be sent an invitation by email, using templates that have already been pre-approved as part of SHARE (REC reference: 20/SS/0048). The email will include a web-based link to the Participant Information Sheet (PIS), the PAINSTORM Dundee Epidemiology questionnaire and to the PAINSTORM website. Participants will be given contact information for the research team if they wish to discuss the study before completing the questionnaire. Participants will also be given contact information to request a paper version of the questionnaire and this will be sent by post along with paper versions of the PIS, invitation letter and a pre-paid envelope.

Where an email address is not held for a participant, they will be contacted by telephone, using a pre-approved SHARE script, and invited to participate either by completing the questionnaire online or by completing a paper questionnaire. If the participant requests to complete the questionnaire online, an email will be sent to them as described above. If the participant requests a paper questionnaire, this will be sent by post along with a paper version of the PIS, an invitation letter and pre-paid envelope. Participants will be given contact information if they wish to discuss the study before completing the questionnaire.

Where both an email address and phone number are not held for a participant, they will be contacted by way of a letter sent through the post. The letter will use a template that has been pre-approved as part of SHARE. Participants will be invited to participate either by completing the questionnaire online or by completing a paper questionnaire. If the participant requests to

complete the questionnaire online, an email will be sent to them as described above. If the participant requests a paper questionnaire, this will be sent by post along with a paper version of the PIS, an invitation letter and pre-paid envelope. Participants will be given contact information if they wish to discuss the study before completing the questionnaire.

As part of the baseline questionnaire, participants will be asked whether they are interested in taking part in a follow-up questionnaire, approximately 18 months after the first. Those that respond yes will be invited by the study team (via HIC) to take part in the follow-up questionnaire, using the same contact methods as the baseline questionnaire.

#### Cohort 3

People on the GoDARTS register who responded to two questionnaires for the DOLORisk Dundee study (REC reference: 15/YH/0285) will be contacted. Participant contact information is held confidentially and securely by the joint GoDARTS/SHARE administration team.

Potential participants will be invited to take part by email (if an email address is held) or by telephone (if an email address is not held). The email will include web-based links to the Participant Information Sheet (PIS), the PAINSTORM Dundee Epidemiology questionnaire and to the PAINSTORM website. Participants will be given contact information if they wish to discuss the study before completing the questionnaire. Participants will also be given contact information to request a paper version of the questionnaire, and this will be sent by post along with paper versions of the PIS, cover letter and a pre-paid envelope.

Where an email address is not held for a participant, they will be contacted by telephone and invited to participate either by completing the questionnaire online or by completing a paper questionnaire. If the participant requests to complete the questionnaire online, an email will be sent to them as described above. If the participant requests a paper questionnaire, this will be sent by post along with a paper version of the PIS, an invitation letter and pre-paid envelope. The invitation letter will contain instructions on how to access the web based PIS, questionnaire and PAINSTORM website. Participants will be given contact information if they wish to discuss the study before completing the questionnaire.

Where both an email address and phone number are not held for a participant, they will be contacted by way of a letter sent through the post. The letter will use a template that has been pre-approved as part of SHARE. Participants will be invited to take part either by completing the questionnaire online or by completing a paper questionnaire. If the participant requests to complete the questionnaire online, an email will be sent to them as described above. If the participant requests a paper questionnaire, this will be sent by post along with a paper version of the PIS, an invitation letter and pre-paid envelope. Participants will be given contact information if they wish to discuss the study before completing the questionnaire.

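### The rule for people on both registers sends them all to Cohort 3, but Cohort 3 admits only two-time DOLORisk responders, so the rest have no valid route into the study as written

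*Protocol*

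**What the plan says.** Section 7.1.1 (Cohort 2) has HIC match the two registers before invitations go out: "HIC will identify people who are participants in both GoDARTS and SHARE, to ensure that those people are not included in the study twice". The routing rule follows: "If someone is included in both registers, they will be invited to take part as per Cohort 3". Its only condition is being on both registers.

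Cohort 3 is narrower than the GoDARTS register. Section 6.1 admits "People on the GoDARTS register (Cohort 3) who responded to two questionnaires for the DOLORisk Dundee study", and the Cohort 3 part of section 7.1.1 repeats the limit for who is approached: "People on the GoDARTS register who responded to two questionnaires for the DOLORisk Dundee study (REC reference: 15/YH/0285) will be contacted". Section 5 describes a much larger register, which "has consented patients with type 2 diabetes (over 10,000 individuals) and matching controls (over 8,000 individuals"), and counts 1,046 participants, all with diabetes, who completed DOLORisk at both time points.

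Cohort 2 has no such limit. Section 6.1 admits "People on the SHARE register (Cohort 2) with Diabetes Mellitus and/or who have received potentially neurotoxic chemotherapy for the treatment of cancer", subject to the age, re-contact consent, vital status and contact-detail conditions shared with Cohort 3. Section 6.2 on exclusions reads "Cohorts 1, 2 & 3: Nil". Belonging to GoDARTS is therefore no bar to Cohort 2.

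**The concern.** The diversion rule depends on register membership, while Cohort 3 eligibility depends on DOLORisk response. Most GoDARTS members satisfy the first and not the second. A SHARE member with diabetes or past neurotoxic chemotherapy who is in GoDARTS but did not answer both DOLORisk questionnaires is eligible for Cohort 2, is moved out of it, and then fails the Cohort 3 criterion. No sentence returns that person to Cohort 2.

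Two things are at stake. The first is the Cohort 2 yield, if the planned numbers were counted before the diversion. The second is the integrity of Cohort 3, if such people are admitted regardless. They would breach its inclusion criterion, and section 11.5 does not permit enrolling people who fail the eligibility criteria. They would also lack the two DOLORisk waves that section 7.4 uses as the Cohort 3 baseline and 18-month data.

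The chemotherapy group is the more sensitive one because its frame is only 600, and section 3.4 assigns the EORTC-CIPN20 to the Cohort 2 chemotherapy group alone. That shows vulnerability. It does not show that a loss has occurred.

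**Working it through.** **Planned yields reproduced (section 8.1).** Frame × response rate:
- Diabetes: 18,000 × 0.333 = 5,994.
- Chemotherapy: 600 × 0.333 = 199.8, i.e. 200.
- Total: 5,994 + 200 = 6,194, which matches the study summary.

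The yields come from the whole frames. No deduction for GoDARTS overlap is shown, and the protocol does not say whether 18,000 and 600 were counted after one.

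**Share of GoDARTS that can enter Cohort 3 (section 5).** 1,046 / 10,000 = 10.46% of members with diabetes. Because the denominator is given as a minimum, this is a maximum, and at least 1 − 0.1046 = 89.5% of diabetic members do not qualify.

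**Routing, case by case, for a SHARE member who meets the Cohort 2 criteria:**

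| Also in GoDARTS? | Both DOLORisk questionnaires? | Route under 7.1.1 | Meets that cohort's criterion in 6.1? |
|---|---|---|---|
| No | – | Cohort 2 | Yes |
| Yes | Yes | Cohort 3 | Yes |
| Yes | No | Cohort 3 | No |

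The third row is the defect. Only the second row could produce double inclusion.

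**Size, by assumption only.** Let M be the number of people in the SHARE diabetes frame who are also in GoDARTS. The protocol does not give M. Two calculations are possible:
- Floor: people without a route ≥ max(0, M − 1,046), which supposes that every two-time responder is on SHARE.
- Average rate: M × 0.8954, which supposes that the overlap responded to DOLORisk at the rate of all diabetic GoDARTS members.

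Expected respondents are each result × 0.333.

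| Assumed M | Floor: people / respondents | Average rate: people / respondents |
|---|---|---|
| 0 | 0 / 0 | 0 / 0 |
| 1,000 | 0 / 0 | 895 / 298 |
| 1,800 (10% of 18,000) | 754 / 251 | 1,612 / 537 |
| 4,500 (25% of 18,000) | 3,454 / 1,150 | 4,029 / 1,342 |

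For M = 1,800 the floor is 1,800 − 1,046 = 754, and 754 × 0.333 = 251, or 251 / 5,994 = 4.2% of the planned diabetes sample. None of the values of M comes from the protocol.

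**If such people are admitted to Cohort 3 instead.** Section 14.1 gives Cohort 3 two historical DOLORisk waves and one new questionnaire at month 72. Someone without both DOLORisk waves would bring one new questionnaire and at most one earlier wave. That one questionnaire can inform presence of NeuP, which is part of the primary objective (section 3.3), and case-control status for the genetic analysis (section 8). It cannot give onset or remission from the planned baseline and 18-month waves.

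**The case against.** The best defence is purpose. The sentence before the rule says the match exists to prevent anyone being included twice, and only a person eligible for both cohorts can be. Read that way, the rule covers two-time DOLORisk responders only. HIC performs the match and, by section 9.1, already hosts the DOLORisk data, so it could apply the narrower filter. This reading is plausible and may be what was intended. It is not what is written, and an extract built from the written rule would omit the others without anyone noticing.

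The defence is stronger on size. A reader might infer that Cohort 2 stands to lose a large part of its sample, up to half: (10,000 − 1,046) × 0.333 = 2,982 of 5,994. The documents do not support that, for four reasons:
- It is not a bound. The 10,000 is a minimum, the controls are left out, and every remaining diabetic GoDARTS member would have to be on SHARE, alive and contactable.
- The 89.5% describes all diabetic GoDARTS members. SHARE members volunteered for research contact, so two-time response may be commoner among them.
- The 33.3% is the baseline GoDARTS response in DOLORisk. The people at issue did not complete both DOLORisk surveys, so some may already have declined or dropped out, and their response may be lower.
- If 18,000 and 600 already exclude GoDARTS members, the targets of 5,994 and 200 are not at risk at all.

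A reader might also infer that diverted people would be useless to the study or that the results would be biased. Neither follows. One wave still serves the presence and case-control analyses. Section 8.4 declares all outcomes exploratory, section 8.2 sets no power target that a smaller Cohort 2 would miss, and no estimate has been shown to be biased.

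**Conclusion.** The inconsistency stands. As written, section 7.1.1 diverts on register membership, section 6.1 admits on DOLORisk response, and no text covers people who meet the first condition and not the second. Followed literally, the plan either drops people who are eligible for Cohort 2 or enrols people who fail the Cohort 3 criterion.

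That most diabetic GoDARTS members fall outside Cohort 3 (at least 89.5%) follows from the protocol's own counts. The number of SHARE members affected does not. It is zero if the overlap is empty or consists only of two-time responders, and even a sizeable overlap leaves the planned yields intact if the frames are already net. The 754 people and roughly 250 respondents at an assumed overlap of 1,800 illustrate scale and are not an estimate. The point needs correcting because the written rule is wrong and cheap to repair. It does not rest on a demonstrated shortfall.

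**What to change.** Replace the routing sentence in section 7.1.1 with one that uses the Cohort 3 criterion: people on both registers who completed both DOLORisk questionnaires are invited as Cohort 3, and all other people on both registers who meet the Cohort 2 criteria are invited as Cohort 2. This still prevents double inclusion. At most 1,046 people would then leave the Cohort 2 frame, each with a valid place in Cohort 3.

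In section 8.1, state the number of people on both registers, separately for the diabetes and chemotherapy frames, and say whether 18,000 and 600 (and so 5,994 and 200) are net of those diverted to Cohort 3. If they are not, restate the yields.

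The cost is one reworded sentence, one added statement and one changed filter in the HIC extract. HIC already runs the match, so the overlap count comes with it. The change is best made before invitations go out, because people left out of the baseline mailing are hard to add to the same wave later.
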